Adolescent anorexia nervosa is a severe eating disorder related to long-lasting morbidity and premature mortality (1, 2), and recent reports from hospitals suggests the prevalence in Norway may be increasing (3). The manualised family therapy “Family Based Treatment” (FBT) is currently the treatment approach for adolescent anorexia nervosa with the largest evidence base (4). FBT is recommended as a first line treatment in multiple service contexts (5, 6).

While there has been conducted several randomised controlled trials of FBT in academic settings (7), there are few large studies examining outcomes when FBT is implemented in clinical practice. A

systematic review published in 2015 found five such dissemination studies. Of these, three were conducted in academic clinical settings with the number of patients ranging from 11 to 20, and two were retrospective studies reporting changes in service use patterns after implementation of FBT in a regular mental health service (8). Two later studies have compared the outcomes achieved in clinical trials of FBT to those of FBT provided in regular clinical care, finding these to be comparable (9, 10), but these have both been conducted in highly specialised clinical contexts. More studies with higher power are needed to confirm the effectiveness of FBT when disseminated to regular healthcare contexts.

At the Child and Adolescent Mental Health Service (CAMHS) unit Nedre Romerike BUP, adolescent anorexia nervosa has consistently been treated with family therapy for about 20 years. In 2018 the unit implemented FBT, making several changes to the form of family therapy provided. As part of treatment monitoring, patients are weighed regularly, and weight data are recorded in patient health records.

Restrictive eating and corresponding weight loss are core features of anorexia nervosa, besides distorted views of the body and rigid preoccupation with losing weight and avoiding weight gain. Normalisation of eating behaviour and weight status is hence the primary treatment goal, making the patient health records in this case contain relevant outcome data.

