The long-term course of anorexia nervosa is heterogeneous, and in some patients the disorder shows a protracted course, with long term morbidity and functional impairment, as well as increased mortality (11). There are few longitudinal studies of treatment outcomes with long follow-up periods (12). As Norway has a general system of personal identification numbers, following up patients across multiple public registries is a viable way to assess long term outcomes without the patients needing to participate in reporting.

AIMS

The primary aim is to assess the short and long-term effectiveness of FBT compared with non-manualised family therapy. This is operationalised as testing whether the adoption of FBT has led to patients achieving normalisation of weight faster than with the previously delivered family therapy, and whether it will lead to less treatment provided for eating disorders in adulthood. Secondary aims are to assess whether adoption of FBT have resulted in reduced time to discharge, changed the heterogeneity of weight gain across patients, whether there have been changes in the rates of adverse events and readmissions, and to assess whether the implementation of FBT has led to changes in long-term functional status and rate of mortality.

DESIGN AND METHODS

Participants and recruitment

This is a two-group retrospective exploratory cohort study with prospective longitudinal follow-up in public registries. Eligible participants are all patients initiating treatment during the years 2015-2020 with the eating disorder team at Nedre Romerike BUP with a primary ICD-10 diagnosis of F50.0 Anorexia nervosa or F50.1 Atypical anorexia nervosa. Patients will be excluded if they were treated during the years 2018-2020 and FBT was never initiated. It is estimated that the final sample size will be approximately 200.

Eligible participants will be identified through review of patient health records. Participants will be contacted by letter with information about the study, including a link to an online video explaining more about the study. Study personnel will make a follow-up telephone call approximately a week later to allow the eligible participant to ask any questions they may have before deciding on participation in the study. Participants who are interested in participating will be directed to a website

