where they can sign an electronic consent form and complete a short survey about their experience of treatment. The consent form and treatment experience survey will be implemented in “Tjenester for Sensitive Data”, which has appropriate security and allows for verified electronic signatures.

Participants will be contacted after they have reached age 16, and thus are able to give informed consent. They will be encouraged to discuss participation with their parents or other legal guardians.

Endpoints and data collection

Primary endpoint for the retrospective study is weight restoration, defined by patients having a weight measurement placing them at or above 95% of expected body weight (50. percentile) for age given Norwegian population norms, following established definitions of weight restoration (10).

Secondary endpoints are discharge from treatment and readmission to treatment (the latter is assumed to be right-censored).

Adverse events will be defined as debut of suicidal ideation, attempted suicide, debut of self-harming behaviour, severe self-harm where medical attention is indicated, hospitalisation for low weight or medical complications from low weight, admission to inpatient treatment for anorexia nervosa, involuntary gastric tube feeding, parental separation, and initiation of contact with child protective services.

Participant experiences and satisfaction with services will be assessed using the Generic Short Patient Experiences Questionnaire (GS-PEQ) (13).

The primary endpoint for the prospective study is continued morbidity, defined as being currently in treatment in specialist health care for any eating disorder. Secondary endpoints are mortality, level of education and employment status.

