We will evaluate whether adoption of FBT has led to faster weight normalisation by fitting a parametric survival model to the number of days until weight restoration is achieved. We will also fit models with gender, age, baseline weight, comorbid disorders and family structure as covariates, and further investigate whether any of these act as moderators of FBT compared with previous treatment. Similar parametric survival models will also be used for modelling differences in time to discharge and readmission. Differences in the rate of adverse events will be modelled using Poisson regression.

We will also evaluate differences between the cohorts in treatment course by fitting multilevel spline models to weight data with knots for every 4 weeks in treatment. Weight measurements will be nested within patients, and patients nested within cohorts. Spline models will allow for modelling non-linear weight change over the course of treatment, and the multilevel structure at the patient level will allow us to evaluate changes in heterogeneity of treatment response pre and post adoption of FBT, as well as visualise trends and heterogeneity of weight change across the course of treatment.

Analysis of prospective data will use parametric survival models or logistic or ordinal regression models, depending on the level of time specificity available in the data.

We have conducted simulations to investigate statistical power, assessing the type S (sign) and type M (magnitude) error rates, given inference based on the posterior median. We made the assumption of achieving at least a sample size of 150 patients and that implementation of FBT has led to a 10% increase in the probability of an event (i. e. weight restoration or discharge). With 1000 simulations, we estimated a type S error of 0.00 and an M error of 0.89, suggesting a very low risk of estimating the sign of the effect incorrectly and a small risk of underestimating the effect size. We conclude that the study will be adequately powered to achieve its primary aim.

The analysis will employ weakly informative prior distributions, using previous studies and other external knowledge (for instance about the biological limits of weight gain per day) to construct priors that rule out impossible areas of the parameter space (17).

ETHICAL CONSIDERATIONS

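### Time to any discharge is read as a benefit, so a cohort losing more unrestored patients looks better on it; handling of such discharges in the primary model is unstated.

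*Combined protocol and SAP*

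**What the plan says.** The primary analysis fits a "parametric survival model to the number of days until weight restoration is achieved" (Analysis plan). The event is "patients having a weight measurement placing them at or above 95% of expected body weight" for age (Endpoints and data collection). The weights come from routine monitoring: "patients are weighed regularly, and weight data are recorded in patient health records" (Background).

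For the other time-to-event outcomes, "Similar parametric survival models will also be used for modelling differences in time to discharge and readmission". Discharge is not divided by weight status or by reason. The data collection text lists the date of discharge for extraction but no reason for it.

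On direction, the Aims state: "Secondary aims are to assess whether adoption of FBT have resulted in reduced time to discharge". The power paragraph likewise treats restoration and discharge alike, as events that FBT makes 10% more probable. The Summary is neutral and asks only whether time to discharge has changed.

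The only statement on censoring is in Endpoints and data collection: "Secondary endpoints are discharge from treatment and readmission to treatment (the latter is assumed to be right-censored". It covers readmission. No censoring or competing-event rule is given for weight restoration, and no proportion or cumulative incidence restored is planned.

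**The concern.** Discharge mixes two opposite outcomes: leaving because weight is restored, and leaving while still underweight. In a model of time to any discharge, both shorten the time. If more patients in one cohort leave unrestored, that cohort looks better on a named secondary aim, even if restoration is no faster and fewer patients restore in treatment.

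The primary endpoint has a related gap. Weights are collected during treatment, so a patient discharged unrestored is normally no longer observed. If such patients are censored, the model estimates restoration as though they would have gone on to restore like those who stayed. That is a legitimate description of speed, but it does not show how many patients actually restored in treatment, and no other planned output does.

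**Working it through.** **Inputs.** The documents give no drop-out, restoration or discharge rates, so the plan has no figure of its own to reproduce on this point. All rates below are assumptions. Hazard ratios (HR) compare FBT with previous treatment; above 1 means earlier.

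**Step 1: hand check with constant hazards.** Take a restoration hazard r = 0.07 per month in both cohorts, and drop-out before restoration d = 0.04 (FBT) v 0.01 (previous), unrelated to prognosis, over 36 months.

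Proportion restored in treatment = r/(r+d) × [1 − exp(−(r+d) × 36)].
- FBT: 0.07/0.11 × [1 − exp(−3.96)] = 0.636 × 0.981 = 62%.
- Previous: 0.07/0.08 × [1 − exp(−2.88)] = 0.875 × 0.944 = 83%.

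The restoration curve with drop-outs censored is 1 − exp(−0.07 × 36) = 1 − exp(−2.52) = 92% in both cohorts, with HR 1.00. A Weibull fit to time to any discharge (mean of 4 months from restoration to discharge assumed) gives HR 1.47 for FBT. So the discharge model favours the cohort with 62% restored, and the censored primary model shows no difference.

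**Step 2: simulation with mixed prognosis.** There are 100,000 patients per cohort and the same restoration process in both: daily hazard log(2)/180 times a lognormal frailty (SD 0.6), with discharge 120 days after restoration. Unrestored discharge is tuned to 25% (FBT) v 10% (previous). Weibull models are fitted, with drop-outs censored in the restoration model.

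| Who leaves unrestored | Discharge HR | Restoration HR | Restored in treatment at one year |
|---|---|---|---|
| Mainly slow gainers | 1.43 | 1.06 | about 65% v 70% |
| Unrelated to prognosis | 1.33 | 1.01 | about 63% v 70% |
| Mainly fast gainers | 1.24 | 0.97 | about 61% v 69% |

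In the first row the median time to discharge is 224 v 268 days, and the censored one-year restoration curve reads 75% v 74%. Reversing the drop-out fractions in that row gives a discharge HR of 0.71, so better retention under FBT would look like slower discharge.

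**Step 3: size against sampling error.** With equal cohorts, SE(log HR) ≈ √(4/events).
- 150 events: √(4/150) = 0.163. 100 events: √(4/100) = 0.20.
- Discharge: ln 1.43 = 0.358, and 0.358/0.163 = 2.2 SE; ln 1.24 = 0.215, and 0.215/0.163 = 1.3 SE.
- Restoration: ln 1.06 = 0.058, which is 0.29 to 0.36 SE.

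**Step 4: a harsher assumption.** Half the patients gain slowly and half fast (restoration hazards 0.03 and 0.15 per month). If drop-out among slow gainers is 0.08 v 0.01 per month, the restoration HR is 1.24 and the discharge HR 1.93, with 61% v 77% restored by 36 months. At 0.06 v 0.02 they are 1.13 and 1.49, with 63% v 72% restored. If instead fast gainers leave at 0.08 v 0.01, they are 0.87 and 1.11, with 61% v 75% restored.

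**Step 5: which remedy works.** In the first row of Step 2, a cause-specific model for discharge after restoration still gives HR 1.23 for FBT (1.13 in the second row). Only patients not yet restored can drop out unrestored, so censoring them leaves a risk set enriched with restored patients awaiting discharge. The cumulative incidence of restored discharge at one year is 56% v 59%, which is the right direction.

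**The case against.** A reader might infer that the plan censors unrestored discharges in the primary model. It does not say so. The plan is silent, other handling is possible, and the extraction of weights is not stated to stop at first discharge.

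A reader might also infer that more drop-out makes FBT look faster on both endpoints, or gives the primary result the wrong sign. The documents do not support that. The restoration HR stays near 1 when drop-out is unrelated to prognosis and falls below 1 when fast gainers leave. The larger distortion in Step 4 needs an eightfold difference in drop-out concentrated among slow gainers. The stated aim is speed of restoration; where both cohorts share one restoration process, an HR near 1 is the right answer to that question. The cumulative incidence answers a different one.

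Nor do the documents imply that drop-out differs by cohort. Earlier discharge could simply follow earlier recovery, and 25% v 10% is assumed.

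Finally, the study is labelled exploratory, and readmissions, low-weight hospitalisations, spline weight courses and registry follow-up could expose premature discharge.

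These points limit the claim on the primary endpoint. They leave the discharge endpoint untouched, because its distortion appears whoever leaves. None of the other analyses corrects either estimate or reports the proportion restored.

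**Conclusion.** The point stands for the discharge endpoint and, in a narrower form, for the primary one. Given unequal unrestored discharge, time to any discharge favours the cohort that loses more patients: HR about 1.24 to 1.43 at an assumed 25% v 10%, with no difference in the restoration process. At about 150 events that is 1.3 to 2.2 standard errors, enough to change a conclusion.

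For restoration, the finding is an unstated rule. If the default is censoring, the HR shifts modestly (0.97 to 1.06 under the same assumption), in either direction, and a one-year deficit in restoration of roughly 5 to 8 percentage points goes unreported. All sizes depend on assumed rates and an assumed time from restoration to discharge. The analysis should be changed before results are seen; confidence is moderate because the real drop-out rates are unknown.

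**What to change.** Derive one variable from the weights and dates already extracted: whether the patient had met the restoration definition by the discharge date.

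1. **Primary endpoint.** Keep the survival model for speed of restoration. State how discharge before restoration is handled, and whether weights recorded after discharge count. Beside the model, report the cumulative incidence of restoration at 6 and 12 months by cohort, with unrestored discharge as a competing event.
2. **Discharge endpoint.** Report the cumulative incidence of restored discharge and of unrestored discharge by cohort, each as a competing event for the other. Interpret reduced time to discharge as a benefit only if the cumulative incidence of restored discharge is higher. Do not rest that claim on a cause-specific hazard ratio alone.

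The cost is a derived variable and a few outputs, with no new data. Intervals for unrestored discharge will be wide: at 75 per cohort and the assumed rates, 0.25 × 75 + 0.10 × 75 ≈ 26 such events. The split is also only a proxy for planned discharge versus drop-out, since a planned discharge just below 95% counts as unrestored and a drop-out just above it as restored. The report should say so.

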Data for the retrospective part of the study will be extracted from electronic patient health records. Weight data will be extracted directly from the electronic patient health record system (DIPS). One researcher will further go manually through all records of included patients and extract dates of treatment start, adverse events, discharge and any readmission, as well as checking the record for any weight measurements recorded but not entered into the weight database. As covariates we will also extract age, sex, gender, family structure, extent of care benefits received during treatment (pleiepenging), and comorbid disorders (ICD-10 diagnoses). Another researcher will independently extract data from a random 10% subsample for control and reliability assessment of coding.

Each participant will be assigned a random case identity number, which will be used for identification in all dataset files when data is analysed. Participant national identity numbers will be stored along with the corresponding case identity number in a separate file, the identity key file. Access to the identity key file will be restricted to the project manager and researchers performing data extraction. It will also be delivered to the agencies maintaining the relevant public registries.

When extracted, data will be entered directly into a REDCap database maintained by Akershus university hospital. Access will be restricted to researchers in the project group. Data will be stored and analysed de-identified.

Data for the prospective part of the study will be acquired from the following public registries: Norwegian Patient Registry, Norwegian Cause of Death Registry, and the databases “Attachment to employment, education and welfare benefits” and “Educational attainment of the population” collated by Statistics Norway. Data will be acquired from these databases in three waves; five, ten and twenty years after the last participant initiated treatment. All registry data will be acquired, stored and analysed de-identified.

Analysis plan

Statistical analysis will be conducted in a Bayesian framework using the Stan platform through the R (14) package brms (15).

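### Adverse events are modelled with plain Poisson regression and no dispersion term; if the listed items are summed per patient, the interval for the cohort rate ratio may be too narrow

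*Combined protocol and SAP*

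**What the plan says.** The Aims section names as a secondary aim "whether there have been changes in the rates of adverse events and readmissions". Under Endpoints and data collection, nine event types are listed in one definition: "Adverse events will be defined as debut of suicidal ideation, attempted suicide, debut of self-harming behaviour, severe self-harm where medical attention is indicated", then "hospitalisation for low weight or medical complications from low weight, admission to inpatient treatment for anorexia nervosa, involuntary gastric tube feeding", and finally "parental separation, and initiation of contact with child protective services". From the records, a researcher will "extract dates of treatment start, adverse events, discharge and any readmission".

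The whole model specification, under Analysis plan, is: "Differences in the rate of adverse events will be modelled using Poisson regression". Neither that section nor any other gives a dispersion parameter, a patient-level effect for this model, a robust variance, a dispersion check, an exposure term or a counting unit. Patient-level multilevel structure is planned, but only for the weight splines. The same section says of discharge: "Similar parametric survival models will also be used for modelling differences in time to discharge and readmission". The length of treatment is therefore treated as something that may differ between the cohorts.

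**The concern.** Poisson regression ties the variance of the count to its mean. Two features of the list can break that tie if items are added up within a patient. First, one episode can meet several definitions. A low-weight admission may also score as inpatient treatment and tube feeding, and one act may satisfy both parts of "debut of self-harming behaviour, severe self-harm where medical attention is indicated". The wording permits this but does not require it. Second, patients may differ in underlying risk.

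A Bayesian fit does not remove the problem. The Poisson likelihood still fixes the variance, and weakly informative priors do not loosen it. At stake is the study's comparison of harms: a chance difference between cohorts, in either direction, could look firmer than the data allow.

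A smaller, linked gap is that a rate needs a denominator, and the time at risk is not stated.

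**Working it through.** **Nothing to reproduce.** The plan gives no adverse-event rate, precision or power. Its type S (0.00) and type M (0.89) figures concern weight restoration or discharge.

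**Inputs from the documents.** Nine items; Poisson regression; a minimum of 150 patients, taken here as 75 v 75 (the equal split is an assumption).

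**Assumed inputs.** No true cohort difference. In total 0.5 episodes per patient, in two episode types of three items each. This simplifies the list, which has four suicidality and self-harm items. Two independent once-only family items at 15% each. Heterogeneity is a gamma multiplier on the episode rate: none, shape 2 or shape 1. The interval is a nominal 95% Wald interval on the log rate ratio, standing in for the posterior interval.

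**Formulas.** Let φ = variance/mean of the per-patient count. The correct standard error is √φ times the Poisson one. A nominal 95% Poisson interval excludes no difference with probability 2[1 − Φ(1.96/√φ)] when there is none.

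**Baselines by hand (no overlap, no heterogeneity).**
- Each item counted at most once: item probability q = 1 − exp(−0.25/3) = 0.080. The mean is 6q + 0.30 = 0.780 and the variance is 6q(1 − q) + 2(0.15)(0.85) = 0.441 + 0.255 = 0.696, so φ = 0.89.
- Episode items allowed to recur: φ = (0.5 + 0.255)/(0.5 + 0.30) = 0.755/0.80 = 0.94, and false exclusion is about 4%.

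In both, Poisson is slightly conservative.

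**Simulation, items summed, each counted at most once** (4000 null runs per cell). The split is the percentage of episodes scoring 1/2/3 items. Entries are for no / shape 2 / shape 1 heterogeneity. The negative binomial (NB) uses a moment-estimated dispersion, which approximates the brms fit.

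| Split | φ | Poisson false exclusion, % | NB false exclusion, % |
|---|---|---|---|
| 100/0/0 | 0.89 / 1.00 / 1.10 | 3.9 / 4.4 / 6.4 | 3.8 / 4.0 / 5.1 |
| 90/10/0 | 0.99 / 1.10 / 1.21 | 4.5 / 6.7 / 7.7 | 4.2 / 5.4 / 5.4 |
| 80/15/5 | 1.16 / 1.28 / 1.38 | 6.5 / 8.0 / 9.6 | 4.8 / 4.6 / 5.7 |
| 60/30/10 | 1.35 / 1.48 / 1.60 | 8.8 / 10.0 / 11.7 | 5.3 / 4.9 / 5.3 |
| Equal thirds | 1.68 / 1.84 / 1.96 | 13.8 / 13.9 / 17.0 | 5.9 / 4.8 / 5.7 |

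The formula agrees: φ = 1.21 gives 1.96/1.10 = 1.78, about 7.5%; φ = 1.96 gives 1.96/1.40 = 1.40, about 16%. The mean log rate ratio stayed within 0.011 of zero, so the point estimate is not biased. A maximum-likelihood NB fit in three of these settings (600 runs each) gave 4.2%, 5.7% and 4.7%, against 7.0%, 11.7% and 16.0% under Poisson.

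**Other counting units.** One count per episode: φ = 0.95 / 1.09 / 1.25, Poisson 4.4 / 6.0 / 7.0%. A single once-only item at 5 / 10 / 30% (8000 runs, both cohorts with at least one event): Poisson 0.6 / 2.8 / 1.6%, which is conservative.

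**A structurally different check.** Take nine yes/no items with common probability p and pairwise correlation ρ, so that φ = (1 − p)(1 + 8ρ). Overdispersion starts at ρ = p/[8(1 − p)]: 0.007, 0.014 and 0.031 for p = 0.05, 0.10 and 0.20. Across those p, coverage of a nominal 95% Poisson interval is 91–94% at ρ = 0.05 and 87–90% at ρ = 0.10. At ρ = 0 it is 96–97%.

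**Exposure.** If true rates were equal and FBT time at risk were 20% shorter (an assumption), the events-per-patient ratio would be 0.80 and the per-time ratio 1.00. This is arithmetic, not evidence about this study.

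**The case against.** The strongest reply is that the real gap is the unstated counting unit, not the model family. No sentence says that items are summed, and for single once-only items or one count per episode Poisson does well. This stands as a condition on the point. It does not dispose of it: the nine items form one definition, the model is for the rate of events so defined, and summing is a natural reading that nothing excludes.

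The plan also sets no interval level or decision threshold, and its simulations base inference on the posterior median. The 5% benchmark is therefore only a calibration yardstick. Interval width still governs how firmly a harms difference is reported.

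This is a secondary aim of a self-described exploratory study, and adverse events are not among the formally listed secondary endpoints. A dispersion check could be added at analysis, though nothing commits to one. These facts limit the weight of the point.

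Finally, a dispersion term widens the interval but does not stop one admission being scored several times. That is correct, and the fix has to address it.

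Two stronger readings are tempting. A reader might infer that the interval will be too narrow whatever is counted; the no-overlap cases contradict this. A reader might also let every item recur and reach larger error figures. Two items are defined as debuts and cannot recur, and no section supports the extreme overlap that such figures need.

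**Conclusion.** The concern holds conditionally. If items are summed per patient, plain Poisson can give too narrow an interval for the cohort rate ratio. Under the stated assumptions with items capped at one, false exclusion is about 4–8% when at most 10% of episodes score two items. It reaches about 17% only when a third of episodes score three items and heterogeneity is strong. If repeatable items recur, the range starts at φ of about 0.94 (4%); the documents support no particular upper figure. Event rates, overlap and heterogeneity are all assumptions, because the protocol gives none. The primary endpoints are untouched. The change is still worth making before analysis, because the alternative model costs little and stays at 4–6% throughout the table.

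**What to change.** In the Analysis plan:

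- State whether items are summed, counted per episode or modelled singly, and which time counts as at risk. If items are combined, give a written definition of an episode, so that one admission is not scored several times unintentionally.
- For per-patient counts, use a negative binomial model, or Poisson with a patient-level random effect, in brms, with a posterior predictive check of dispersion.
- For repeatable events, add log time at risk as an offset, built from the dates already being extracted. For once-only items, model time to first event.
- Report events per patient as well, because treatment length may itself differ between cohorts.

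The cost is a change of model family, a few sentences, and slightly more analysis work, with no new data. Standard errors would be about 1.0–1.4 times the Poisson ones in the item-capped cases. Without overlap or heterogeneity almost nothing is lost (3.8% v 3.9% false exclusion).
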